#### 9.1.20 Documentation of Randomization

Only subjects who meet all of the inclusion criteria and none of the exclusion criteria are eligible for randomization into the treatment phase.

If the subject is found to be not eligible for randomization, the investigator should record the primary reason for failure on the applicable eCRF.

## 9.1.21 Assessment of Suicidal Ideation and Behavior

The C-SSRS was developed by researchers at Columbia University as a tool to help systematically assess suicidal ideation and behavior in subjects during participation in a clinical trial of centrally-acting drugs. The C-SSRS is composed of 3 questions addressing suicidal behavior and

5 questions addressing suicidal ideation, with subquestions assessing the severity. The tool is administered via interview with the subject.

#### **SRD**

The Screening/Baseline C-SSRS will be administered at Screening and Check-in (Day -1) and the Since Last Visit C-SSRS will be administered on discharge Day 5 and Study Exit Day 7 or Early Termination.

#### SRD/MRD

The Screening/Baseline C-SSRS will be administered at Screening and Check-in (Day -1) and the Since Last Visit C-SSRS will be administered on Day 11, and Study Exit (Day 21) or Early Termination.

## 9.2 Monitoring Subject Treatment Compliance

Study drug will be administered while subjects are under observation in the clinical research unit. Following administration of the study drug, appropriate mouth and/or hand checks will be performed to ensure that the dose is swallowed and noted in the source document. The date and time of each dose will be recorded in the source documents and on the eCRFs. An inventory of the study drug supplies dispensed will be performed by the site pharmacist or authorized study designee and recorded onto the Drug Accountability Log in the subject's source document records or equivalent. The exact dose time of consecutive subjects may be staggered to facilitate logistics at the site.

#### 9.3 Schedule of Observations and Procedures

The schedule for all study-related procedures for all evaluations is shown in Appendix A. Assessments should be completed at the designated visit/time point(s). Additional assessments may be conducted or timing of existing assessments may be amended based on emerging safety, PK or PD data.

#### 9.3.1 Screening

Subjects will be screened within 28 days prior to randomization, in accordance with predefined inclusion and exclusion criteria as described in Section 7.0. See Section 9.1.19 for procedures for documenting screening failures.

Procedures to be completed at Screening (all cohorts) include the following:

- Informed consent.
- Inclusion/exclusion criteria.
- Demographics, medical history, and medication history.
- Physical examination (including a comprehensive neurological examination-details in Appendix G).

- Vital signs.
- Weight, height, and BMI.
- Concurrent medical conditions.
- Screening clinical laboratory tests.
- Hepatitis panel.
- FSH (postmenopausal women).
- Serum pregnancy test (hCG) (all female subjects).
- Pregnancy avoidance counseling.
- Urine drug screen and alcohol breathalyzer.
- ECG procedure.
- EEG assessments.
- C-SSRS (Baseline/Screening version).
- PTE assessment.

In the event that subjects have undergone general screening assessments (ie, panel screening) before the effective date of this protocol amendment, the data from this general screening may be used to assess subject eligibility for enrollment in this study, provided that the procedures were performed within the protocol-defined Screening Period window.

#### 9.3.2 Check-In Procedures

Procedures to be completed at Check-in (Day -1) include the following:

## **SRD Cohorts**

- Inclusion/exclusion criteria assessments.
- Physical examination, including complete neurological examination (see Appendix G).
- Vital signs.
- Weight.
- Concomitant medications.
- Concurrent medical conditions.
- Clinical Laboratory tests.
- Urine pregnancy test (hCG) (all female subjects).
- Urine drug screen.
- Alcohol breathalyzer.

- ECG.
- EEG.
- C-SSRS (Baseline/Screening version).
- PTE assessments.

#### **SRD/MRD Cohorts**

- Inclusion/exclusion criteria assessments.
- Physical examination, including complete neurological examination (see Appendix G).
- Vital signs.
- Weight.
- Concomitant medications.
- Concurrent medical conditions.
- Clinical laboratory tests.
- Urine pregnancy test (hCG) (all female subjects).
- Urine drug screen.
- Alcohol breathalyzer.
- ECG.
- C-SSRS (Baseline/Screening version).
- PK urine collection.
- PTE assessments.

#### 9.3.3 Treatment Phase

Procedures to be completed during the treatment phase include the following:

#### **SRD Cohorts**

- Vital signs.
- Telemetry (36 hours postdose).
- Concomitant medications.
- Clinical laboratory tests (Days 1, 2, 5).
- ECG procedures (Days 1, 2, 5).
- CC
- C-SSRS (Day 5) (Since Last Visit version).

- DNA (Day 1) and RNA (Days 1, 2) sample collections.
- PK blood collections.
- blood collections (Days 1-5; SRD Cohort 6 onward only).
- Dispense study medication (Day 1).
- PTE assessments (Day 1 predose).
- AE assessments.

#### **SRD/MRD Cohorts**

- Vital signs.
- Concomitant medications.
- Clinical laboratory tests (Days 1, 6, 9, 12, 15, 18).
- ECG procedures (Days 1, 6, 9, 12, 15, 18).
- CCI
- C-SSRS (Day 11) (Since Last Visit version).
- DNA (Day 1) and RNA (Days 1 and 18) sample collections.
- PK blood collections (Days 1-7, 12, 14, 16, 18-19).
- collections (Day 12, SRD/MRD Cohort 3 only).
- blood collections (Days 1-5, 18, 19; SRD/MRD Cohort 3 onward only).
- PK urine collections (Days 1-4, 18-19).
- Dispense study medication (Day 1, Days 6-18).
- PTE assessments (Day 1 predose).
- AE assessments.

#### 9.3.4 Study Exit

Procedures to be completed by all Cohorts at Study Exit (SRD Cohorts 1-5 on Day 7, SRD Cohort 6 onward on Day 8, SRD/MRD on Day 21) include the following:

- Physical examination, including complete neurological examination (described in Appendix G).
- Vital signs.
- Weight.
- Concomitant medications.

- Clinical laboratory tests.
- Serum pregnancy test (hCG).
- Pregnancy avoidance counseling.
- ECG.
- EEG assessments.
- C-SSRS (Since Last Visit version).
- PK blood collections (SRD only).
- AE assessments.

For all subjects receiving study drug, the investigator must complete the End of Study eCRF page.

## 9.3.5 Early Termination

The reason for discontinuation must be documented in the source document and eCRF. All of the procedures listed in Section 9.3.4, Study Exit, should be performed with the following differences:

- EEG assessments should be performed at early termination.
- PK blood collection is not required at early termination in either SRD or SRD/MRD.

For all subjects receiving study drug, the investigator must complete the End of Study eCRF page.

#### 9.3.6 Follow-up Call/Visit

Follow-up assessments are scheduled to occur on Day 14 (±2 days) for SRD subjects and Day 31 (±2 days) for SRD/MRD subjects to inquire for any ongoing AEs or SAEs, worsening of AEs or SAEs, or development of new AEs or SAEs, and for concomitant medications taken since final dose.

Subjects with unresolved SAEs, CS laboratory abnormalities, ECG or physical examination findings or at the investigator's discretion should return to the clinic for appropriate repeat procedure(s). A follow-up phone call will be made to all other subjects on Day 14 (±2) for an assessment of AEs and concomitant medications.

#### 9.3.7 End-of-Trial Date

The End-of-Trial date will be based on the final data collection date for the entire study, which is the date of the last Follow-up call/visit.

#### 9.4 Blood Volume

Total blood sampling volume for an individual subject in the SRD Cohorts is shown in Table 9.f.

Table 9.f Approximate Blood Volume: SRD Cohorts 1 to 5

	Cample		Nur	nber o	f Samp	oles pe	r Sub	ject			
Sample Volume	Study Day									Total Volume	
Sample Type	(mL)	Screening	-1	1	2	3	4	5	6	7	(mL)
Safety Laboratory (a)	10	1(b)	1	1	1			1		1	60 (110 for food-effect cohort)
PK	4			13	2	1	1	1	1	1	80 (160 for food-effect cohort)
CCI	6			1							6
CCI	2.5			6	2						20
	ı	ı			Total	Blood	Samp	ling V	olume	(mL)	166 (296 for food-effect cohort)

-- = no samples collected.

Table 9.g Approximate Blood Volume: SRD Cohort 6 Onward

Sample Type	Comple	Number of Samples per Subject										
	Sample Volume			Total Volume								
	(mL)	Screening	-1	1	2	3	4	5	6	7	8	(mL)
Safety Laboratory (a)	10	1	1	1	1			1			1	60
PK	4			13	2	1	1	1	1	1	1	84
CCI	4			4	1	1	1	1				32
CCI	6			1								6
CCI	2.5			6	2							20
Total Blood Sampling Volume (mL)								202				

-- = no samples collected.

The maximum volume of blood collected per subject on any single day is approximately 99 mL, and the approximate total volume of blood per subject in SRD Cohorts 1 to 5 is 166 mL and in SRD Cohort 6 onward is 202 mL. Subjects in the food effect cohort will have participated twice, once under fasted conditions and again under fed conditions. Therefore, the total volume of blood per subject in the food effect cohort will be approximately 296 mL. These totals do not include overage (eg, repeat samples, discard blood volume).

Total blood sampling volume for an individual subject in the SRD/MRD Cohorts is shown in Table 9.h.

a) No blood is collected on Days 3, 4, and 6 for safety laboratory assessments.

b) For the food effect cohort, blood will be collected for safety laboratory collections only once at Screening.

a) No blood is collected on Days 3, 4, 6, and 7 for safety laboratory assessments.

**Table 9.h** Approximate Blood Volume: SRD/MRD Cohorts

		Number of Samples per Subject																
	Sample		Study Day															
Sample Type	Volume So	Volume	Screen- ing	-1	1	2	3-5	6	7	9	12	14	15	16	18	19	21	Total Volume (mL)
Safety Laboratory	10	1	1	1	-	-	1	-	1	1		1		1		1	90	
PK	4			13	2	3	9	1		2 (a)	1	-	1	13	1		184	
CCI (b)	4			4	1	3								4	1		52	
CCI	6			1	-	-	-	-									6	
CCI	2.5			2	-	-	-	-						2			10	
	1	1								To	tal B	lood S	Sampl	ing Vo	lume	(mL)	342	

-- = no samples collected.

The maximum volume of blood collected per subject on any single day in the SRD/MRD is approximately 89 mL and the approximate total volume of blood collected per subject is 342 mL. These totals do not include overage (eg, repeat samples, discard blood volume).

Direct venipuncture is the preferred method of blood collection. Any other method will need to be approved by Takeda. If an intravenous cannula with a normal saline flush is used, the total blood volume does not include discarded blood from predraws (assuming approximately 3 mL of blood is discarded each time a sample is collected from an intravenous cannula).

a) An additional PK sample will be taken following the CCI collection procedure in SRD/MRD Cohort 3 only.

b) Collected only for SRD/MRD Cohort 3 onward.

#### 10.0 PRETREATMENT EVENTS AND ADVERSE EVENTS

#### 10.1 Definitions

#### 10.1.1 PTEs

A PTE is defined as any untoward medical occurrence in a clinical investigation subject who has signed informed consent to participate in a study but prior to administration of any study drug; it does not necessarily have to have a causal relationship with study participation.

#### 10.1.2 AEs

An AE is defined as any untoward medical occurrence in a clinical investigation subject administered a drug; it does not necessarily have to have a causal relationship with this treatment.

An AE can therefore be any unfavorable and unintended sign (eg, a clinically significant abnormal laboratory finding), symptom, or disease temporally associated with the use of a drug whether or not it is considered related to the drug.

#### 10.1.3 Additional Points to Consider for PTEs and AEs

An untoward finding generally may:

- Indicate a new diagnosis or unexpected worsening of a pre-existing condition. (Intermittent events for pre-existing conditions underlying disease should not be considered PTEs or AEs.)
- Necessitate therapeutic intervention.
- Require an invasive diagnostic procedure.
- Require discontinuation or a change in dose of study drug or a concomitant medication.
- Be considered unfavorable by the investigator for any reason.
- PTEs/AEs caused by a study procedure (eg, a bruise after blood draw) should be recorded as a PTE/AE.

Diagnoses vs signs and symptoms:

• Each event should be recorded to represent a single diagnosis. Accompanying signs (including abnormal laboratory values or ECG findings) or symptoms should NOT be recorded as additional AEs. If a diagnosis is unknown, sign(s) or symptom(s) should be recorded appropriately as PTE(s) or as AE(s).

Laboratory values and ECG findings:

• Changes in laboratory values or ECG parameters are only considered to be PTEs or AEs if they are judged to be clinically significant (ie, if some action or intervention is required or if the investigator judges the change to be beyond the range of normal physiologic fluctuation). A laboratory re-test and/or continued monitoring of an abnormal value are not considered an

- intervention. In addition, repeated or additional noninvasive testing for verification, evaluation or monitoring of an abnormality is not considered an intervention.
- If abnormal laboratory values or ECG findings are the result of pathology for which there is an overall diagnosis (eg, increased creatinine in renal failure), the diagnosis only should be reported appropriately as a PTE or as an AE.

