## 6.3 Premature Termination or Suspension of Study or Investigational Site

#### 6.3.1 Criteria for Premature Termination or Suspension of the Study

The study will be completed as planned unless one or more of the following criteria are satisfied that require temporary suspension or early termination of the study.

- New information or other evaluation regarding the safety or efficacy of the study drug that indicates a significant change in the known risk/benefit profile for the drug, such that the risk is no longer acceptable for subjects participating in the study.
- Significant violation of Good Clinical Practice (GCP) that compromises the ability to achieve the primary study objectives or compromises subject safety.
- Study-specific criteria for terminating the study:
  - a) Subjects in more than 1 cohort have met Cohort Stopping Criteria.
  - b) Any subject in any cohort experiences signs or symptoms of a tremor. (Subjects may not be dosed in this cohort at the same or higher dose level. However, dosing may be resumed at a lower dose level.)

The study may be terminated early prior to full attainment of these criteria (eg, if just 1 subject experiences 1 of these events), if warranted by safety data from the other subjects dosed in the study to that point.

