## 10.1.5 Adverse Events of Special Interest

An adverse event of special interest (AESI) (serious or non-serious) is one of scientific and medical concern specific to the compound or program, for which ongoing monitoring and rapid communication by the investigator to Takeda may be appropriate. Such events may require further investigation in order to characterize and understand them and would be described in protocols and instructions provided for investigators as to how and when they should be reported to Takeda.

Based on nonclinical data to date and AMPA receptor potentiator class effects, the AESIs for this study are:

- Tremors.
- Convulsions.

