## 10.2.1.3 AESI Reporting

If an AESI that occurs during the treatment period or the follow-up period is considered clinically significant based on the criteria below, it should be recorded in an AESI Form or an SAE Form. The Form should be completed and reported to the clinical contract research organization (CRO)/Pharmacovigilance (PV) department within 24 hours.

AESI / abnormality criteria include:

- Laboratory value threshold, if applicable.
- Premature termination for the AESI, if applicable.
- Tremors.
- Convulsion.

The standard query form in the eCRF is to be completed for tremors and convulsions. All other AESIs must be recorded as AEs in the eCRF. An evaluation form along with all other required documentation must be submitted to the sponsor.

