7.9.1 Adverse Events

A TEAE will be defined as an AE or a SAE that occurs or gets worse after receiving the first dose of study drug and within 30 days (onset date – last date of dose + $1 \le 30$) after the last dose of study drug. A TEAE may also be a pretreatment event (PTE) or a concurrent medical condition diagnosed prior to the date of first dose of study drug that increases in severity after the start of dosing. Adverse events data with onset occurring more than 30 days after last dose of study drug (AE start date – last dose date >30) will be listed, but not included in the summary tables.

AE verbatim reported terms will be coded by system organ class (SOC), high-level term (HLT) and preferred term (PT) using MedDRA.

The following is a list of AE summary tables that will be generated:

- Overview of TEAE.
- TEAEs by SOC and PT at subject and event level.
- Subject Mappings for TEAEs.
- TEAEs by PT.
- Non-Serious TEAEs by PT.

- Relationship of TEAEs to Study Drug by SOC and PT.
- Drug-Related TEAEs by SOC and PT.
- Intensity of TEAEs by SOC and PT.
- Intensity of Drug-Related TEAEs by SOC and PT.
- PTEs by SOC and PT
- Serious PTEs by SOC and PT.

A subject with 2 or more different AEs within the same level of the MedDRA term will be counted only once in that level using the most extreme incident for the intensity tables, and relationship to study drug for the causality tables.

Data listings will be provided for all AEs (including PTEs for enrolled subjects), AEs leading to study drug discontinuation, AEs leading to study visit discontinuation, SAEs, and AEs resulting in death.

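### A tremor that accompanies a recorded diagnosis can be missing from the only planned tables of tremor by dose, because 10.1.3 and 10.2.1.3 do not require it to be entered as its own AE

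*Protocol*

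**What the plan says.** **Recording rule.** Protocol 10.1.3 wants each event recorded as a single diagnosis: "Accompanying signs (including abnormal laboratory values or ECG findings) or symptoms should NOT be recorded as additional AEs". The same bullet limits this. When no diagnosis has been established, the sign or symptom is itself entered as a PTE or AE.

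**AESIs.** Protocol 10.1.5 says "Based on nonclinical data to date and AMPA receptor potentiator class effects, the AESIs for this study are" tremors and convulsions. There are two, and they are not ranked.

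**AESI reporting.** Under Protocol 10.2.1.3, for an AESI judged clinically significant by the listed criteria (which include tremors and convulsion), "it should be recorded in an AESI Form or an SAE Form", sent within 24 hours. It continues: "The standard query form in the eCRF is to be completed for tremors and convulsions". The next sentence reads: "All other AESIs must be recorded as AEs in the eCRF".

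**General AE documentation.** Protocol 10.2.1.2 sends all PTEs and AEs to the PTE/AE page of the eCRF, with term, dates, severity and causality.

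**Analysis.** SAP 7.9.1 introduces its outputs with "The following is a list of AE summary tables that will be generated". Eleven tables follow, built from TEAEs or PTEs by overview, SOC, preferred term, relationship and intensity. None is for AESIs, and none draws on the AESI or query forms.

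**The concern.** Tremor is a sign, and it is one of only two events the sponsor singled out in advance. Read literally, 10.1.3 tells an investigator who diagnoses, say, anxiety or a convulsion with accompanying tremor to enter the diagnosis alone. One would expect the AESI section to override this. Instead, the only sentence there that requires AESIs to be recorded as AEs covers AESIs other than tremors and convulsions, which is an empty set.

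At stake is the description of tremor by dose. Protocol 6.2.4 names tremors among the key risks from the nonclinical findings. The rule works in one direction only: it can lower the tabulated number of subjects with tremor and cannot raise it. A tremor left off the AE page also has no severity or causality of its own in the AE dataset, so it drops out of the intensity and relationship tables too.

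**Working it through.** The plan gives no figure to reproduce here; SAP section 6.0 says the sample size was not based on power. The check sets the passages side by side and then does simple arithmetic.

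**1. Where each kind of event goes**

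- *Tremor, no known diagnosis.* 10.1.3 requires an AE entry. It appears in the preferred-term tables. No gap.
- *Tremor accompanying a recorded diagnosis.* 10.1.3 keeps it off the AE page. 10.2.1.3 puts it on an AESI or SAE form and on the query form, but does not say that it also goes on the AE page. The tables show the diagnosis row only. This is the gap.
- *Convulsion.* Convulsive seizure is in the medically significant list (Protocol Table 10.a), so it is an SAE under 10.1.4 and would normally be the diagnosis itself. The exposure is therefore mainly for tremor, although the wording of 10.2.1.3 covers both.

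**2. Whether another SAP output counts tremor**

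- SAP 7.9.5: shift tables of EEG interpretation. These do not count tremor.
- SAP 7.9.6: neurological examination results, listed only.
- SAP 7.1: raw and derived data listed as appropriate. Query-form data may be listed under this, but are not summarised.

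So the SAP 7.9.1 tables are the only planned summaries in which tremor by dose would appear.

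**3. Size**

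Inputs: 6 active subjects per cohort (SAP 6.0); 5 SRD/MRD cohorts (SAP 4.4 table). Rate = x/n, with exact (Clopper-Pearson) 95% intervals.

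- One subject with tremor, tabulated: 1/6 = 16.7% (0.4% to 64.1%).
- Same subject, tremor absorbed into a diagnosis and no other tremor recorded: 0/6 = 0% (0% to 45.9%).
- Two subjects with tremor: 2/6 = 33.3% (4.3% to 77.7%). This becomes 1/6 if one is absorbed, and 0/6 only if both are.
- Pooled TAK-653 in Part 2: 5 × 6 = 30 active, so one subject is 1/30 = 3.3%.

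The intervals overlap widely. What changes is the visible count at a dose, not an inferential result. The documents give no basis for estimating how often absorption would happen, so these are sizes per affected subject and not expected losses.

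**4. What does not move**

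- *At least one TEAE.* The subject still counts through the recorded diagnosis, provided that is itself a TEAE.
- *Stopping criteria.* Item (b) of Protocol 6.3.1 reads "Any subject in any cohort experiences signs or symptoms of a tremor", and cohort criterion 3 likewise turns on a tremor developing. Neither refers to an entry on the AE page. Protocol 9.1.13 also requires an EEG after any tremor.

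**The case against.** The strongest reply is that tremor is already treated as an event in its own right. Section 10.1.5 classes it as an adverse event of special interest, 10.2.1.2 sends every AE to the AE page, and a specific AESI provision can reasonably be read as overriding a general rule on diagnoses and symptoms. Subjects are healthy, with clinically significant neurologic, psychiatric and endocrine disease excluded. The most informative case, a drug-induced tremor with no competing diagnosis, therefore reaches the AE page under the same bullet of 10.1.3. Recorded tremors are then tabulated by preferred term, intensity and relationship, so a separate AESI table may look like a preference.

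Most of this stands, and it confines the gap to tremor that accompanies a recorded diagnosis. It does not close it. The override has to be inferred, and the one sentence that could have stated it is worded the other way. Section 10.2.1.2 does not help either, because 10.1.3 decides what counts as a separate AE in the first place.

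Three stronger readings are tempting, and the documents do not support them:

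- *Tremor is lost from the study.* It is not; the AESI or SAE form and the query form hold it.
- *A stop could be missed.* Section 6.1.3 does say that reported AEs are evaluated against the termination criteria, but it also requires review of all safety data for each completed cohort, and the criteria depend on tremor occurring. At most, the stopping record and the AE tables could disagree.
- *The absence of CNS-type AEs reported in section 4.3 is an artefact of the rule.* Nothing in the documents shows that any tremor was left out.

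**Conclusion.** The point holds in limited form. The recording rule and the AESI sentence together leave it unclear whether a tremor accompanying a diagnosis must be its own AE, and the SAP has no other summary that would show it. For each affected subject with no other recorded tremor, a dose-level row falls by one in six. The bias can only be downward.

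This assumes that investigators follow 10.1.3 as written and do not infer an AESI exception, and that a diagnosis is recorded to which the tremor is attached. The frequency of that situation is unknown and may be low in healthy volunteers. Neither the primary TEAE percentage nor any stopping decision is shown to change. This is a cheap improvement, not a threat to the study's conclusions.

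**What to change.** 1. **Protocol 10.1.3:** add one sentence saying that every tremor and convulsion is entered as a separate AE, with its own onset, severity and causality, even when it accompanies another diagnosis.
2. **Protocol 10.2.1.3:** reword the sentence on other AESIs so that tremors and convulsions go on the AE page as well as on the AESI or SAE form and the query form.
3. **SAP 7.9.1:** add one table giving the number and percentage of subjects with tremor or convulsion, by TAK-653 dose level and pooled placebo within each part, reconciled with the AESI, SAE and query forms. Because it draws on forms the protocol already requires, it also covers cohorts already dosed, as far as those forms were completed.

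The cost is two short protocol edits and one table. The downside is some double counting in event-level totals, where a tremor and its accompanying diagnosis would both appear; a footnote can say so. No clinical rule changes.
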